### **Mixed methods data analysis.**

At the 3-month follow up assessment, we will use additional open-ended questions at the end of the assessment to explore why and how the participants did or did not successfully quit smoking and stay abstinent. Specifically, for participants who were biochemically confirmed abstinent, the questions will focus on what motivated them to quit and how they overcame challenges or barriers to stay abstinent. For participants who were not abstinent, the questions will focus on why they did not or could not quit, what they underwent, what challenges or barriers they had, and what would help them quit in the future.

Two research team members will perform qualitative data coding with the aid of the R-QDA. Discrepancies will be discussed to achieve intercoder agreement. Codes and quotations will be arranged into focused themes (i.e., thematic content analysis) to develop the mixed methods data inventory. Next, we will examine quantitative (RCT) and qualitative data jointly, using the **integration strategy of explaining** with the intent to explore why participants could or could not quit and stay abstinent. Mixed methods linked data, results, and meta-inferences will be presented in visual joint displays, similar to our previous publication.

Identifiers might be removed and the de-identified information may be used for future

### **Data analysis.**

Descriptive statistics will be used to assess **feasibility** of AT. Regarding **preliminary efficacy** of AT, we will use log-binomial regression with an intent-to-treat approach (i.e., missing=smoking) to compare the effect of the treatment on the dichotomous abstinence outcome at 12 weeks post-enrollment, controlling for selected covariates such as sex, education level, and/or baseline stress level. Secondary outcomes will be examined using appropriate linear and generalized linear mixed models with log-binomial and linear regression for binary and continuous variables, respectively. Given the

research without additional informed consent from the subject.

## **E. CHART REVIEW**

As described above, at the in-clinic assessments at baseline and at 3-month follow-up, the Lao research team will also collect data from participants' medical records (in addition to interview data and expired air CO assessment). Medical records will be used to collect clinical information, such as comorbidities, recent/current diagnosed health conditions, and current use of medications for AT personalization. In Lao PDR, most of these medical records/data are in paper form; thus, the Lao research staff will review the records/forms and will enter data into the standardized sections/questions in REDCap Mobile app. The tablets that contain the REDCap app are password protected, encrypted, and can be remotely wiped if lost.

## **F. BIOSPECIMEN**

This project does not collect biospecimen.

## **G. BANKING/REPOSITORY/DATABASE**

This project does not bank or store data for future use in other projects.

## **H. INCLUSION/EXCLUSION CRITERIA**

**Inclusion criteria.** The pilot RCT will include those who are 1) aged  $\geq 18$  years; 2) self-reported current combustible cigarette smokers (smoked at least 100 cigarettes in lifetime and currently smoke  $\geq 1$  cigarette/day); 3) willing to set a quit date within 2 weeks of study enrollment; 4) able to provide written informed consent to participate; and 5) able to read Lao (score  $\geq 4$  points on the Rapid Estimate of Adult Literacy in Medicine—Short Form^51).

**Exclusion criteria** are 1) history of a medical condition that precludes use of NRT; 2) ineligibility to participate based on medical or psychiatric conditions diagnosed by a physician/clinician; and 3) enrollment in another cessation program or current use of other cessation medications. With these criteria in our Cambodian pilot study, we recruited 2–5 participants per day; thus, we expect a similarly high consent rate and feasibility for this study.

## **I. GENDER/MINORITY/PEDIATRIC INCLUSION FOR RESEARCH**

### **I1. Inclusion of Women**

We will recruit a pilot sample that mirrors the national smoking prevalence in men and women. Specifically, we will ensure that female smokers are represented in our sample in a manner that aligns with the smoking prevalence by sexes in the real-world. All participants, including men and women, will be encouraged to continue their participation in the study.

### **I2. Inclusion of Minorities**

An attempt to enroll all eligible participants will be made without regard to race/ethnicity. Because this project will take place in Lao PDR, we expect that all participants will be Asian. Among these, approximately 90% will be of Lao ethnicity, 5% will be of other ethnicities (e.g., Chinese, Vietnamese, Thailand), and 5% will be multi-ethnicity. As with all participants, the recruited minority participants will be encouraged to continue their participation in the study.

### **I3. Inclusion of Children**

We have excluded children under the age 18 from the proposed study. In Lao PDR, 18 is the age of majority and, therefore, participants aged  $\geq 18$  years can consent. We excluded smokers under the age of 18 because the safety of nicotine replacement therapy (NRT) has not been determined for this population. The US Food and Drug Administration has not approved the use of NRT for smoking cessation for children and adolescents.

## J. RECRUITMENT AND ENROLLMENT

Cancer survivors (n=40) or caregivers (n=40) of both sexes who smoke will be recruited from SH and LNCC in Vientiane (the capital of Lao PDR). At SH, the Department of Oncology and Department of Breast and Gynecologic Cancer serve >200 cancer patients each year. LNCC serves >400 new patients with various types of cancer each year. Research staff will review medical records of cancer patients receiving care at the 2 hospitals in the past 2 years, screen for their smoking status documented in the records, and contact those who smoked for further screening. To recruit caregivers, research staff will contact random cancer patients who **did not** smoke and ask if they have a caregiver and if the caregiver smokes. Given the pilot nature of this study, we propose to recruit independent groups of cancer survivors and caregivers who smoke, i.e., no dyads of smokers, to avoid potential interpersonal interactions.

## K. RISKS AND BENEFITS

### K1. Potential Risks

The risks to participants are generally minimal and include breach of confidentiality, emotional distress (due to the nature of the assessment questions), and side effects associated with NRT patch use.

There are minimal potential risks to participants from the personal nature of the questions asked regarding health behaviors and health status. Answering the questions may cause participants to feel uncomfortable and/or upset.

Problems associated with the use of nicotine patches include local skin irritation at the site of application, nausea (if the dose of the patch is too high or if high levels of smoking are continued while using the patch), and distressing dreams. Skin allergic reactions have been less commonly reported. Participants may experience unpleasant withdrawal symptoms following smoking cessation. These symptoms include anxiety, restlessness, anger, irritability, sadness, difficulty concentrating, change in appetite, weight gain, insomnia, and decreased heart rate.

### K2. Protection against Risks

**Protection against Confidentiality Breach:** Confidentiality will be maintained for all data and contact information. To protect against the risk of a confidentiality breach, the following steps will be taken:

- REDCap will be used to collect and manage information for most procedures, including screening eligible participants, administering in-clinic assessments at baseline and follow-ups, and capturing participants' information from medical records. REDCap is a secure web-based application designed to comply with all HIPAA regulations. Data will be collected by participants (e.g., self-interviews for baseline assessment) or by research staff (e.g., screening or reviewing medical records) on tablets using the REDCap Mobile App. Each participant will be given a unique identification number (UIN) in this study, and the UIN will be used in all data collection procedures that are managed by REDCap. The REDCap Mobile App employs encryption at-rest on the mobile device's hard drive so that all important data and information stored on the device are properly protected from unauthorized or malicious users. All data are transmitted between the app and the OUHSC secure REDCap server using a secure, encrypted transmission

(SSL/HTTPS). REDCap has been used by several institutions in Lao. The tablets are password protected, encrypted, and can be remotely wiped if lost.

- All data related to participants will be identified only by the UIN. A master list of participant UINs linked to participant names will be stored in locked file cabinets in locked study offices at SH or CH. Access to the master list will be limited to those with privileges. After completion of the study and data analysis, the identification file will be destroyed.
- Participants will not be identified in any public reports or documents. In qualitative component reports, if any, only participant initials or random initials will be used for quotations. In the trials, only aggregate data will be reported and released. At no time will individual names appear in any report, article, or manuscript related to the study.
- To minimize risks related to participant information potentially being disclosed via the use of smartphones, the following features are designed to ensure the security of the assessment data:
  - o The data stored on the smartphone device is in a SQLite database in a sandbox environment, where read/write operations are only available through the programming application (i.e., no file or output is readable to end users).
  - o A 10-character password (only known to researchers) is required to authenticate the current user before data can be manually accessed on the smartphone.
  - o Encrypted smartphone data will be automatically sent to our OUHSC mHealth Shared Resource secure servers multiple times per day.
  - o The web browser application linking the investigator's computer to the database uses HTTPS protocol (SSL certificate with encryption), which will guarantee the protection of data transferred from the web browser to the backend database.
  - o The backend database is hosted by the OUHSC mHealth Shared Resource in a secure setup.
  - o Software will be downloaded onto each study phone so that phones can be remotely wiped if lost.
- During the consent process, participants will be informed of the potential for psychological distress or discomfort associated with unintentional disclosure of personal information to non-study staff, and the nature of the questions to be asked will be made clear.
- Participants will be informed of the safeguards in place and encouraged to contact investigators at any time to discuss any confidentiality concerns that arise.

**Protection against Coercion:** All recruitment contacts will emphasize the voluntary nature of participation. Consent materials will clearly state that participants recruited for the trial will be randomly assigned to 1 of 2 groups and that participation in the study may not be personally beneficial.

**Protection against Assessment-Related or Intervention-Related Discomfort:**

The potential for discomfort associated with being asked personal questions regarding sensitive topics will be minimized in the following ways:

- Participants will be informed of the nature of questions to be asked and topics covered; participants can decline participation if such topic areas are known to be personally uncomfortable.
- Only measures that have been validated or used in prior studies will be used or will be adapted for use in this study. None of the proposed instruments have been known to evoke serious emotional reactivity.

- The use of self-administration for the assessments on a tablet or phone may help participants feel more comfortable in answering sensitive questions.
- Participants can refuse to answer any questions that they do not wish to answer.
- Participants who become distressed by answering questions will be given resources to access help.
- Participants will be reminded during the consent process that they may contact the research staff with any questions or concerns that arise during their participation.
- Participants may choose to discontinue participation at any time.

Those who experience a skin reaction from nicotine patch use will be instructed to move the site of the nicotine patch each day. Additionally, participants will be instructed to wait at least 7 days before using the same site for patch placement. To minimize nausea, participants will be instructed not to smoke while using the patch. If smoking relapse occurs, the participant will be instructed to stop using the patch. Participants experiencing distressing dreams or other sleep interference will be instructed to remove the patch before bedtime. If a severe skin reaction develops, the participant will be instructed to discontinue patch use. Use of the patch should reduce the severity of withdrawal-related symptoms. Withdrawal symptoms are generally short-lived and typically last no more than 2 weeks after smoking cessation. Patches will be dispensed under the supervision of a health care provider.

### **K3. Potential Benefits of the Proposed Research to Human Subjects and Others**

Tobacco smoking is among the leading causes of morbidity and mortality in low- and middle-income countries. Smoking cessation treatment offers tremendous potential to prevent smoking-related morbidity and to reduce overall mortality in this population. The risks to participants are small, and the health benefits of quitting smoking at the individual level are appreciable and well documented.

To our knowledge, no theoretically based tobacco treatment program is available in national public hospitals in Lao PDR. It is also unknown whether mHealth-based smoking cessation approaches that have efficacy in developed countries would be effective in low- and middle-income countries. The results of this study will help Lao governmental health officials implement a potential affordable and sustainable approach for smoking cessation for Laotians that may lead to widespread adoption and also be applicable to other health issues. Thus, this research has the potential to transform healthcare delivery throughout the country.

### **L. MULTIPLE SITES**

Not applicable.

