### Abstract

In Lao People's Democratic Republic (Lao PDR), tobacco smoking prevalence among cancer patients is high: 60% in men and 15% in women. Evidence from developed countries suggests that smoking cessation offers considerable benefits for cancer survivors, including improving cancer treatment outcomes, reducing recurrence rates, reducing second primary tumor development, and reducing overall cancer mortality rates. Despite, ***no tobacco treatment programs are available*** in major (public) hospitals in Lao PDR, including in cancer hospitals/institutions. The parent project (1R21CA253600-01, **OUHSC IRB#: 12189**) aims to adapt and evaluate the efficacy of our theoretically and empirically based mobile health (mHealth) technology to help Lao general patients quit smoking cigarettes. This mHealth automated treatment (AT) approach includes a fully automated, interactive, personalized, smartphone-based intervention for behavioral treatment, delivered through our Insight platform. In year 1 of the parent project, we have been adapting our intervention content to the sociocultural context, language, and communication styles of Laotians. The ***purpose*** of this supplementary project is to expand our mHealth-based AT to ***address the pressing need for smoking cessation among cancer survivors and their caregivers in Lao PDR***. In this project, we will adapt our intervention and materials to make them comprehensible and relevant to these target populations. Next, we will conduct a pilot randomized controlled trial (RCT, N=80) to evaluate the preliminary efficacy of the intervention. Cancer survivors (n=40) and caregivers (n=40) of both sexes who smoke will be recruited at Setthathirath Hospital and Lao National Cancer Center. Similar to the parent project's design, participants will be randomized to 1 of 2 treatment groups: standard care (SC) or AT (20 cancer survivors and 20 caregivers in each group). SC consists of brief advice to quit smoking, self-help written materials, and a 2-week supply of NRT (transdermal patches). AT consists of all SC components plus our fully-automated interactive smartphone-based treatment program, personalized and tailored to cancer survivors or caregivers. The ***primary RCT outcome*** is biochemically confirmed self-reported 7-day point prevalence abstinence at 3 months post-study enrollment. The ***specific aims*** are: 1) to evaluate the feasibility of AT in cancer survivors

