### Stage 2: The pilot RCT

**Participant recruitment.** We will conduct a pilot RCT (N=80) to evaluate the preliminary efficacy of the intervention (*Figure*). Cancer survivors (n=40) or caregivers (n=40) of both sexes who smoke will be recruited from SH and LNCC in Vientiane (the capital of Lao PDR). At SH, the Department of Oncology and Department of Breast and Gynecologic Cancer serve >200 cancer patients each year. LNCC serves >400 new patients with various types of cancer each year. Research staff will review medical records of cancer patients receiving care at the 2 hospitals in the past 2 years, screen for their smoking status documented in the records, and contact those who smoked for further screening. To recruit caregivers, research staff will contact random cancer patients who **did not** smoke and ask if they have a caregiver and if the caregiver smokes. Given the pilot nature of this study, we propose to recruit independent groups of cancer survivors and caregivers who smoke, i.e., no dyads of smokers, to avoid potential interpersonal interactions.

**Inclusion criteria.** The pilot RCT will include those who are 1) aged  $\geq 18$  years; 2) self-reported current combustible cigarette smokers (smoked at least 100 cigarettes in lifetime and currently smoke  $\geq 1$  cigarette/day); 3) willing to set a quit date within 2 weeks of study enrollment; 4) able to provide written informed consent to participate; and 5) able to read Lao (score  $\geq 4$  points on the Rapid Estimate of Adult Literacy in Medicine—Short Form^51). **Exclusion criteria** are 1) history of a medical condition that precludes use of NRT; 2) ineligibility to participate based on medical or psychiatric conditions diagnosed by a physician/clinician; and 3) enrollment in another cessation program or current use of other cessation medications.

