**Figure: Study schema**

With these criteria in our Cambodian pilot study, we recruited 2–5 participants per day; thus, we expect a similarly high consent rate and feasibility for this study.

**Baseline assessment.** Enrolled participants will complete a 45-minute baseline self- or assisted interview, managed and delivered by REDCap. Participants will be randomly assigned to SC or AT by the REDCap randomization module (simple, 1:1). Smartphones will be loaned to participants as needed. All participants will complete a brief training session on smartphone use and the Insight app. The Insight app also includes a help button for instructions on how to use each feature, which participants can review at any time.

**Treatment groups.** SC consists of brief advice to quit smoking delivered by research staff, self-help written materials (the WHO’s “A guide for tobacco users to quit” that we have translated to and validated in Lao), and a 2-week supply of NRT (transdermal patches). AT consists of all SC components plus a fully automated smartphone-based JITAI that involves proactive, interactive, and personalized messages, images, or videos in Lao. Adapted from the parent study and based on the PBM, AT content is designed to increase motivation, self-efficacy, and use of coping skills and reduce nicotine withdrawal symptoms and stress. AT will begin immediately after enrollment and continue for 12 weeks (about 2 messages/images/videos per day, delivered at participants’ preferred time). Quit date is set at day 14 post-enrollment for AT and SC participants. JITAI content for AT participants each week will be **personalized and tailored** to each participant’s **baseline information** (e.g., sex, cancer types, caregiver status, and current health conditions), **current PBM phase**, and **responses to the brief weekly EMAs** that drive AT (see *Measures*). Our AT only targets cigarette smoking because it is the most common type of tobacco used by Lao smokers (95%).

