### **M. STATISTICAL METHODS**

Descriptive statistics will be used to assess **feasibility** of AT. Regarding **preliminary efficacy** of AT, we will use log-binomial regression with an intent-to-treat approach (i.e., missing=smoking) to compare the effect of the treatment on the dichotomous abstinence outcome at 12 weeks post-enrollment, controlling for selected covariates such as sex, education level, and/or baseline stress level. Secondary outcomes will be examined using appropriate linear and generalized linear mixed models with log-binomial and linear regression for binary and continuous variables, respectively. Given the preliminary nature of the RCT, we do not expect to have sufficient power for full hypothesis testing. However, from our previous work, we anticipate that the abstinence at the 12-week follow-up will be 8% in the SC group. With 40 participants in each group, we will have 80% power to detect a difference as small as 20% in

smoking abstinence rates between groups ( $\alpha=0.05$ , one-tailed, unadjusted).

**Mixed methods data analysis.** At the 3-month follow up assessment, we will use additional open-ended questions at the end of the assessment to explore why and how the participants did or did not successfully quit smoking and stay abstinent. Specifically, for participants who were biochemically confirmed abstinent, the questions will focus on what motivated them to quit and how they overcame challenges or barriers to stay abstinent. For participants who were not abstinent, the questions will focus on why they did not or could not quit, what they underwent, what challenges or barriers they had, and what would help them quit in the future.

Two research team members will perform qualitative data coding with the aid of the R-QDA. Discrepancies will be discussed to achieve intercoder agreement. Codes and quotations will be arranged into focused themes (i.e., thematic content analysis) to develop the mixed methods data inventory. Next, we will examine quantitative (RCT) and qualitative data jointly, using the *integration strategy of explaining* with the intent to explore why participants could or could not quit and stay abstinent. Mixed methods linked data, results, and meta-inferences will be presented in visual joint displays, similar to our previous publication.

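### Two hospitals recruit 80 people under simple, unstratified 1:1 allocation, which leaves hospital mix and arm size to chance; stratified blocks would be a minor, cheap improvement

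*Combined protocol and SAP*

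**What the plan says.** All references are to the combined protocol and SAP.

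- **Sites.** Section L (Multiple Sites) reads "Not applicable". Section J says that participants "will be recruited from SH and LNCC in Vientiane (the capital of Lao PDR"), and the recruitment paragraph of Section D, Stage 2, refers to "cancer patients receiving care at the 2 hospitals in the past 2 years".
- **Volumes.** Section J says that the Setthathirath Hospital (SH) departments "serve >200 cancer patients each year". It credits the Lao National Cancer Center (LNCC) with more than 400 new patients a year. No enrolment target by hospital is given.
- **Allocation.** The baseline assessment paragraph of Stage 2 says: "Participants will be randomly assigned to SC or AT by the REDCap randomization module (simple, 1:1"). No stratification factor or block is mentioned.
- **Planned composition.** The Abstract plans "20 cancer survivors and 20 caregivers in each group", and Aim 2 (Section A) evaluates efficacy in each of those subgroups.
- **Analysis.** Section M specifies a log-binomial model "controlling for selected covariates such as sex, education level, and/or baseline stress level". Hospital is not named as a stratum, covariate, random effect or sensitivity analysis.

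**The concern.** Hospital is known for every participant before randomization. It could plausibly relate to abstinence, through the patients each hospital sees or the way staff there give the in-person advice. Simple allocation does nothing to limit a chance difference in hospital mix between arms. Because hospital has no stated place in the model, any difference that arises may stay in the AT-SC estimate, or be adjusted for only after the data have been seen.

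Simple allocation also does not deliver the planned 40 per arm, or the 20 survivors and 20 caregivers per arm on which the subgroup aim rests. At stake are some precision, credibility and consistency with the stated plan. Validity is not at stake.

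**Working it through.** **Plan's own figure.** Section M states 80% power with 40 per arm, 8% abstinence under SC, a 20-point difference (read as 8% v 28%) and one-tailed alpha of 0.05. The arcsine formula gives h = 2·asin(√0.28) − 2·asin(√0.08) = 0.542. Power = Φ(0.542 × √20 − 1.645) = Φ(0.778) = 78%. The pooled-variance formula gives 76%. The claim is approximately reproduced and serves here only as the yardstick.

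**Standard error of the AT-SC difference.** √(0.08 × 0.92/40 + 0.28 × 0.72/40) = 0.083, or 8.3 points.

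**Chance imbalance by hospital.** The documents give no enrolment split. Assume it follows the stated volumes, about 200:400, which gives 27 at SH and 53 at LNCC. With roughly 40 per arm, the SD of the between-arm difference in SH share is about √(0.3375 × 0.6625 × (1/40 + 1/40)) = 0.106. Simulating simple allocation, where arm sizes also vary, gives 0.107.

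| Assumed setting | Difference ≥10 points | Difference ≥20 points |
|---|---|---|
| 80 people, 27/53 | 35% | 6% |
| 80 people, 40/40 | 43% | 9% |
| 40 survivors only, 13/27 | about half | 19% |

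**Effect on the estimate.** Shift = imbalance × between-hospital difference in abstinence. The documents give no hospital-specific rates, so assume a difference of 5 to 20 points.

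- Average over all randomizations (27/53): the mean absolute imbalance is 8.6 points. 0.086 × 5 = 0.4 and 0.086 × 20 = 1.7 points.
- At a 20-point imbalance, the edge of the 6% tail: 0.20 × 5 = 1 and 0.20 × 20 = 4 points.
- Share of sampling variance, (0.107 × hospital effect)² / 0.083²: 0.4% for a 5-point effect, 1.7% for 10 points and 6.7% for 20 points.

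**Arm size and planned composition (binomial, p = 0.5).**

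- Exactly 40/40: 8.9%.
- Arm sizes differing by 10 or more (45/35 or worse): 31%.
- 20/20 in both survivors and caregivers: 0.125² = 1.6%.

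The cost of unequal arms is itself small. At 45 AT and 35 SC the standard error is √(0.0736/35 + 0.2016/45) = 8.1 points; with the sizes reversed it is 8.6.

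**What stratifying by hospital gains.** Simulations used hospital splits of 26/54 and 40/40, SC abstinence of 2-8% at one hospital and 8-13% at the other, and a 20-point effect. Moving from simple allocation with an unadjusted test to stratified allocation with a Mantel-Haenszel test raised power by about 0.3 to 1.0 points. One-sided type I error was 5.1-5.2% before and 5.3-5.8% after.

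**Room for adjustment.** Expected abstainers number 0.08 × 40 + 0.28 × 40 = 3.2 + 11.2, about 14 in all. Any adjustment has to be sparse.

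**The case against.** The strongest case against is that this hardly matters, and most of it stands.

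- Simple randomization is valid, and its standard errors already include chance imbalance. A shift of 1 to 4 points needs both a 6% event and an assumed hospital effect. The upper end of that assumption is strained: with about two thirds of SC at LNCC and 8% abstinence overall, LNCC's SC rate could exceed SH's by at most about 0.08/0.6625 = 12 points.
- A reader might infer that Section L's answer is why hospital was left out of the randomization and the model. No text links them. Section L sits among short administrative headings, one site PI is named in Section N, and both hospitals come under one ministry and one Lao ethics committee. The answer may concern oversight only.
- A reader might infer that the two hospitals have different case mix. No distribution by hospital is given, SH includes a general oncology department, half the sample are caregivers, and sex is already a named covariate.
- A reader might say that hospital is excluded from the model. The covariate list is open-ended, so hospital is unspecified rather than excluded.
- Hospital alone would be the wrong priority. Survivor/caregiver status is the factor for which the plan fixes numbers per arm.

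What remains is that a factor known before randomization goes uncontrolled when control is nearly free, and that the allocation method does not deliver the composition the Abstract describes.

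**Conclusion.** A minor point that holds. Two hospitals recruit, allocation is simple and unstratified, and the role of hospital in the analysis is not stated. Chance imbalance in hospital mix and in arm size is therefore uncontrolled.

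Under the assumed enrolment split and hospital effect, the average shift is about a fifth of a standard error at most (1.7/8.3). The documents do not support calling the comparison biased or invalid, and the expected gain in power is slight. The case for change rests on low cost, on prespecification, and on agreement with the planned 20 survivors and 20 caregivers per arm. Section L needs a wording correction or a clarification of what it covers.

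**What to change.** 1. **Section D, Stage 2, baseline assessment.** Replace simple allocation with REDCap randomization in permuted blocks of varying size, 1:1, stratified by hospital (SH, LNCC) and by survivor/caregiver status. This makes four strata, averaging 20 people each.
2. **Section M, and the matching data-analysis paragraph in Section D.** State how the strata enter the analysis, in a form suited to about 14 expected abstainers. One option is a Mantel-Haenszel risk ratio, at least as a sensitivity analysis. Hospital need not displace education level or another listed covariate. If hospital is to have no role, say why.
3. **Section L.** Reconcile the answer with the two-hospital recruitment text, or say that it refers to oversight arrangements only.

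Cost: a new allocation table and a few sentences. Blocking makes allocation slightly more predictable, which varying the block size limits. Incomplete blocks leave a small residual imbalance. The Mantel-Haenszel test ran slightly above nominal one-sided type I error in the simulations (up to 5.8%), and the precision gained is small.
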